## 6.3 Clinical Laboratory Evaluations

Clinical laboratory evaluations include biochemistry, hematology and urinalysis. Actual values and change from baseline values of continuous laboratory tests will be summarized by treatment group for each visit. For categorical lab tests, frequency and percentage distribution will be presented by treatment group for each visit.

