Subjects to be studied will have histologically confirmed NASH as defined by the NIH NASH CRN (Kleiner 2005) and determined by a qualified central pathologist's reading (see [Appendix 1](#)). Historical biopsy results within 6 months of the first Screening visit may be used for inclusion into the study; otherwise, a liver biopsy must be obtained for assessment. Subjects must have a NAS of at least 4, with a minimum of 1 point in each of the three components, along with the presence of either Stage 2 or 3 fibrosis. Subjects with no (Stage 0) or minimal (Stage 1) fibrosis and cirrhosis (Stage 4) will be excluded from this study. Subjects will undergo MRI during the Screening period, which must demonstrate $\geq 8\%$ total liver fat content (LFC) by MRI-PDFF.

Subjects may be rescreened once with Medical Monitor approval. Note: certain laboratory parameters of interest (e.g., AST, TBL, creatinine clearance) may be retested at the investigators' discretion after discussing with the Medical Monitor.

On Day 1, eligible subjects will be randomized into one of the four treatment groups (0.3 mg aldafermin, 1 mg aldafermin, 3 mg aldafermin, or placebo) in a 1:1:1:1 ratio ([Table 3](#)). Randomization will be stratified by baseline stage of fibrosis (Stage 2 versus 3) on the qualification liver biopsy as determined by the Central Pathologist. Treatment assignment will be blinded to the investigational sites, study subjects, and sponsor (both Study Team and sponsor Medical Monitor or designee) throughout the study period and managed [REDACTED]. Study-drug self-administration instructions and training will be provided to the subjects and study-drug kits will be dispensed.

Table 3. Study Design

Study Treatment Group	Dose of aldafermin ^[1]	Mode of Administration	Volume of Injection ^[2]	Number of Subjects Planned
A	0.3 mg			38
B	1 mg			38
C	3 mg			38
D	Matched-Placebo			38
Total number of Subjects Planned:				152

^[1] In clinic dosing will occur on Day 1 and Study Week 2, 4, 8, 12, 18, and 24.

^[2] Presented in single-use prefilled syringes.

The first dose of aldafermin (Day 1) and doses at Weeks 2, 4, 8, 12, 18, and 24 study visits will be self-administered in the clinic, with all other daily doses through Week 24 self-administered at home. Self-administration should occur daily at a similar time at home. Subjects will return to the clinic on Weeks 2, 4, 8, 12, and 18 for on-treatment assessments and to receive aldafermin study-drug kits.

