iii. Adverse event of muscle symptoms (e.g., myalgia, pain, or weakness) or elevated creatine kinase:

A sample will be collected for assessment of CK within 48-72 hours, and CK assessment will be repeated if needed (refer to [Appendix 5](#)). At Weeks 12 and 24, the creatine kinase (CK) level will be compared to the subject's baseline level.

- If CK level is $\leq 3x$ baseline, subject will continue on aldafermin and over-encapsulated rosuvastatin.
- If CK level is $> 3x$ baseline, CK will be repeated within 48 - 72 hours and aldafermin and rosuvastatin will be held:
 - If CK is $\leq 3x$ baseline, subject can re-start on aldafermin and rosuvastatin based on the investigator's judgement.
 - If CK is $> 3x$ and $< 5x$ baseline, repeat CK levels within 48 - 72 hours while aldafermin and rosuvastatin on hold.
 - If CK is $\geq 5x$ baseline, aldafermin and rosuvastatin will be discontinued.

Upon repeat testing for subjects previously with CK $> 3x$ but $< 5x$ baseline:

- If CK is $\leq 3x$ baseline, subject can re-start on aldafermin and rosuvastatin based on the investigator's judgement.
- If CK level is $> 3x$ baseline, subject will discontinue aldafermin and rosuvastatin.

iv. Laboratory value(s) indicative of DILI:

- a) Elevation of AST or ALT $> 2x$ above subject-specific baseline value (calculated using the average of the Day -42, Day -28 and the Day 1 values) and total bilirubin $> 1.5 \times$ subject-specific baseline value, repeat testing of ALT, AST, and bilirubin must be performed within 48 - 72 hours. If there are persistent elevations (AST or ALT $> 2x$ baseline or TBL $> 1.5x$ baseline values) upon repeat testing, then close observation (testing and physical examination 2 - 3 times per week) should be implemented and discontinuation of aldafermin and rosuvastatin should be considered (see b [below](#)).
- b) A decision to discontinue or temporarily interrupt the study drug will be considered based on factors that include how much higher than baseline ALT and AST were relative to the upper limit of normal (ULN) and how much the on study ALT and AST levels have increased relative to baseline, in addition to whether there is concomitant elevation of bilirubin or INR. Aldafermin and rosuvastatin will be discontinued or temporarily interrupted as follows:
 - If baseline measurements (BLM) were $< 2x$ ULN, discontinue if ALT or AST increases to $> 5x$ BLM
 - If BLM $\geq 2x$ ULN but $< 5x$ ULN, discontinue if ALT or AST increases to $> 3x$ BLM

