- If BLM \geq 5x ULN, discontinue if ALT or AST increases to $> 2x$ BLM
- Discontinue if ALT or AST increase $> 2x$ BLM AND the increase is accompanied by a concomitant increase in TBL to $> 2x$ BLM OR the INR concomitantly increases by > 0.2
- In any subjects with signs and symptoms of fatigue, nausea, vomiting, right upper quadrant pain or tenderness, fever, rash, and/or eosinophilia ($> 5\%$).

- c) If the subject lives in a remote area, laboratory testing can be performed locally and the results should be promptly communicated to the investigator site.
- d) Close observation for suspected DILI will include:
 - Repeating liver enzyme and serum bilirubin tests two or three times weekly. Frequency of repeat testing can decrease to once a week or less if abnormalities stabilize or the study drug has been discontinued and the subject is asymptomatic.
 - Obtaining or re-confirming a detailed history of symptoms and prior or concurrent diseases.
 - Obtaining or re-confirming the history of concomitant drug use (including nonprescription medications and herbal and dietary supplement preparations), alcohol use, recreational drug use, and special diets.
 - Ruling out acute viral hepatitis types A, B, C, D, and E; autoimmune or alcoholic hepatitis; NASH hypoxic/ischemic hepatopathy; and biliary tract disease.
 - Obtaining a history of exposure to environmental chemical agents

Outside of situations listed above no aldafermin /matched placebo dose reductions will be allowed. Temporary drug holidays from aldafermin dosing ≤ 5 days will be allowed on a case by case basis for subjects for safety or tolerability but must be approved by the Sponsor Medical Monitor or designee. If drug is restarted and is still not tolerated, the subject should stop the medication as multiple drug holidays will not be allowed.

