#### 2.2 Data Conventions

The following data conventions will be used for all analyses described in this SAP.

- All subject-level data will be provided in data listings, unless stated otherwise.
- Study day will be calculated as:
  - o visit date first dose date, for screening visits;
  - o visit date first dose date + 1, for post-baseline/treatment visits.
- Baseline value will be defined as the last available, valid, non-missing assessment reported before the start of first study drug administration. The randomization date (and time, if available) will be used if the study drug start date is missing or not available for any reason.
- Change from baseline (change) is calculated as follow-up baseline. Percent (or relative) change from baseline (percent/relative change) is calculated as 100 × (change from baseline/baseline).
- Descriptive statistics including the number of non-missing observations (n), arithmetic mean (mean), standard deviation (SD), median, minimum (min), and maximum (max) will be presented for continuous endpoints. Frequency and percentage distribution will be presented for categorical endpoints. Kaplan-Meier estimates will be presented for time-to-event endpoints if applicable.
- Continuous endpoints will be analyzed using an analysis of variance (ANOVA) or analysis of covariance (ANCOVA) model. Ordinal categorical endpoints will be analyzed using a Wilcoxon rank-sum test. Nominal categorical endpoints will be analyzed using a Pearson's Chi-square test or Cochran-Mantel-Haenszel (CMH) test (A Fisher's exact test will be used if ≥ 25% of the cells have expected counts < 5). Time-to-event endpoints will be analyzed using a (stratified) log-rank test and Cox's proportional hazards model.

- Type III sums of squares will be used for all ANOVA and ANCOVA models.

- The level of statistical significance used for all statistical tests will be 0.05, unless stated otherwise. Statistical hypotheses for the primary efficacy analyses and the associated sensitivity analyses will be tested for statistical significance with two-sided alternatives, and one-sided alternatives will be used for all secondary and other efficacy analyses. All confidence intervals (CIs) will be two-sided, unless stated otherwise.
- Data from unscheduled visits will be presented in data listings, but will not be used for statistical analysis/summaries.

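### No visible SAP summary counts, by arm, the subjects who meet the protocol's own laboratory criteria for liver injury, singly or jointly

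*SAP*

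**What the plan says.** Protocol 8.3, item iv, gives liver rules that apply within a subject.

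- **iv a.** A rise of ALT or AST above 2x the subject's baseline with TBL above 1.5x baseline leads to a recheck: "repeat testing of ALT, AST, and bilirubin must be performed within 48 - 72 hours". The baseline is "calculated using the average of the Day -42, Day -28 and the Day 1 values".
- **iv b.** Drug is stopped or interrupted when ALT or AST exceeds 5x, 3x or 2x the baseline measurement (BLM), according to whether BLM is below 2x ULN, from 2x to below 5x ULN, or at least 5x ULN. A joint rule applies when ALT or AST exceeds 2x BLM and "the increase is accompanied by a concomitant increase in TBL to" more than 2x BLM, or INR rises at the same time by more than 0.2.
- **iv d.** Close observation means "Repeating liver enzyme and serum bilirubin tests two or three times weekly". The frequency may fall to weekly or less once values stabilise, or once drug is stopped and the subject has no symptoms.

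Scheduled visits are sparser. Protocol 7 says: "Subjects will return to the clinic on Weeks 2, 4, 8, 12, and 18 for on-treatment assessments", with the end-of-treatment visit at Week 24.

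SAP 6.3 states: "Actual values and change from baseline values of continuous laboratory tests will be summarized by treatment group for each visit". It gives frequencies only for tests that are categorical in themselves. SAP 5 adds percent change for ALT, AST and TBL as efficacy endpoints. The only ALT/AST count, in SAP 5.2, is of normalisation. Two conventions in SAP 2.2 matter here: "Data from unscheduled visits will be presented in data listings, but will not be used for statistical analysis/summaries" and "Baseline value will be defined as the last available, valid, non-missing assessment reported before the start of first study drug administration".

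**The concern.** Safety and tolerability are among the primary objectives, and the drug is expected to lower mean ALT. A liver signal in a trial of this size would be a few subjects moving against that trend, possibly with bilirubin or INR rising in the same person. The protocol has already defined what such a subject looks like. The visible analysis plan does not carry that definition into any summary.

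The report could therefore show mean ALT falling in every active arm without saying how many subjects per arm met the protocol's criteria, or whether any met the joint ones. A reader would have to rebuild this from listings, choosing a baseline and a handling of unscheduled values after the fact.

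**Working it through.** The plan states no figure on this point, so there is none to reproduce. The check compares the texts and adds small illustrations.

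**1. Which visible outputs could hold the count?**

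- SAP 6.3 and SAP 5: value, change and percent change by visit, for one analyte at a time. No threshold for a rise, no pairing.
- SAP 5.2: ALT and AST normalisation, which is improvement.
- SAP 6.2: adverse events by preferred term, grade, relationship and withdrawal. No laboratory criterion.
- SAP 3.1: discontinuation by primary reason.
- INR: not among the test groups named in SAP 6.3. Protocol 12.6 may cover it as another continuous safety variable, but again on its own.

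None gives a by-arm count of subjects meeting 8.3 iv.

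**2. What the mean shows.** Inputs: 38 subjects per arm (SAP 1.1); a mean ALT change of -35 IU on 3 mg in the earlier 12-week study (Protocol 5.2.2), given to every other subject; baseline B of 70 to 80 IU (assumed). With k subjects at m times baseline:

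mean change = [(38 - k)(-35) + k(m - 1)B] / 38

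For k = 1, m = 3, B = 70: (37 x (-35) + 140)/38 = -1155/38 = -30.4.

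| Case | B = 70 | B = 80 |
|---|---|---|
| One at 3x | -30.4 | -29.9 |
| Three at 3x | -21.2 | -19.6 |
| One at 5x | -26.7 | -25.7 |
| Three at 5x | -10.1 | -7.0 |

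The mean moves but stays negative in every case.

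**3. Pairing.** Express values as multiples of baseline in an arm of 38. Put three subjects at 3x for ALT, three at 2.5x for TBL and everyone else at 1x.

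- ALT mean = (35 + 9)/38 = 1.158, SD 0.547, maximum 3.0.
- TBL mean = (35 + 7.5)/38 = 1.118, SD 0.410, median 1.0, maximum 2.5.

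If the same three subjects carry both rises, three meet ALT above 2x with TBL above 2x. If different subjects carry them, none does. All the summaries above are the same in both cases.

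**4. Unscheduled results.** Visits from Week 12 to Week 24 are 6 weeks apart. Close observation through a whole gap would give 6 x 2 = 12 to 6 x 3 = 18 results. That is an upper case: weekly testing gives about 6, and fewer is allowed. Those falling between visits appear only in listings, as does a 48-72 hour recheck done at an unscheduled visit.

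**5. Baseline (depends on an assumed ULN).** Take ALT of 80, 80 and 60 IU at Day -42, Day -28 and Day 1, and 190 IU on treatment.

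- SAP baseline: 190/60 = 3.17x.
- 8.3 iv a baseline: (80 + 80 + 60)/3 = 73.3, and 190/73.3 = 2.59x.

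Both exceed the 2x of iv a. Under iv b the result differs if, for example, ULN is 30 IU: 60/30 = 2.0 and 73.3/30 = 2.4, so the 3x limit applies to both and only the SAP baseline crosses it. With any ULN above 30, the SAP baseline is below 2x ULN and its limit is 5x, so neither baseline crosses.

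**6. What a count would add.** With 0 cases in 38, the one-sided 95% upper limit on the rate is 1 - 0.05^(1/38) = 7.6%. With 0 in the 114 subjects on active drug it is 2.6%.

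**The case against.** The strongest reply is that nothing planned fails. Protocol 6.1 defines the primary safety endpoint through adverse and serious adverse events. Item 8.3 iv is for managing individual subjects and is not an endpoint. Protocol 12.6 promises descriptive laboratory summaries, and SAP 6.3 delivers them. All of this stands. A reader might infer that the SAP contradicts the protocol or leaves the primary safety endpoint unanalysed; the documents do not support that.

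Nor would a signal be lost. SAP 2.2 puts all subject-level data in listings, and with 38 per arm the joint cases could be found by hand. Protocol 11.1 treats clinically relevant laboratory changes as adverse events, so SAP 6.2 would capture some. That route is weaker than it looks, because ALT and AST are blinded to site and sponsor from Week 2 (Protocol 9.1, Table 4 notes).

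It is also tempting to say the planned tables would hide an outlier. They would not at a scheduled visit, since SAP 2.2 includes the minimum and maximum. At a baseline of 75 IU, one subject at 5x shows a maximum change of +300 and three at 3x show +150. What the maximum lacks is a count and a link between analytes.

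The pairing example holds by construction, since separate summaries never fix a joint count. It shows what the tables cannot say, not how likely joint cases are.

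Finally, the bodies of SAP 6.7, 7 and 10 are not shown, and no table shells are provided. One cannot conclude that the sponsor planned no such output.

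**Conclusion.** The point holds as a minor gap in safety reporting, limited to the visible text. Three features combine: laboratory summaries of one analyte at a time, exclusion of unscheduled results, and a baseline that differs from 8.3 iv a. Together they leave no visible by-arm count of subjects meeting the protocol's liver laboratory criteria, and no summary containing values found between visits.

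The size is modest. The illustrations rest on an assumed baseline ALT of 70 to 80 IU and a constant change in all other subjects; the baseline example rests on an assumed ULN. They show what the planned summaries can and cannot display, and do not predict liver events. No efficacy inference, power or alpha is affected. The case for acting is that the count is cheap and its definitions are better fixed before unblinding.

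**What to change.** Add one table to SAP 6.3, on the Safety set by arm: number and percent of subjects meeting each laboratory threshold of 8.3 iv at any post-baseline assessment, including ALT/AST with TBL and ALT/AST with INR. Specify:

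- **Data.** An explicit exception to SAP 2.2, so that unscheduled results count in this table, and local results too where they are in the database.
- **Baseline.** The three-value average of 8.3 iv a for ALT, AST and TBL, with a statement that it also serves as BLM in iv b, which does not say how BLM is calculated. For INR, the last pre-dose value.
- **Joint timing.** Results from the same collection date. A wider window, such as through the next scheduled visit, would catch bilirubin rising after ALT. It is optional, is not in the protocol, and should be fixed before unblinding if used.
- **Scope.** Laboratory thresholds only; the symptom criterion in iv b is not counted.

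A plot of peak ALT against peak TBL by arm is a useful option.

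The cost is SAP wording and a little more programming. Local results can be counted only if they are captured with their own ULN, which the visible text does not promise.

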## 6.4 Vital Signs, Body Weight, BMI and Waist Circumference

Vital sign assessments include seated systolic/diastolic blood pressure, respiration rate, pulse and temperature. Actual values and change from baseline values for vital signs, body weight, BMI and waist circumference will be summarized by treatment group for each visit.

## 6.5 12-Lead Electrocardiograms

The 12-lead ECG assessments include QT interval, QTcF interval, P-R interval, R-R interval and QRS duration. Actual values and change from baseline values for 12-lead ECG assessments will be summarized by treatment group for each visit. Frequency and percentage distribution of the overall ECG interpretation results (Abnormal, Indeterminate, Normal, Not evaluable, Unknown per CRF) will be presented by treatment group for each visit.

## 6.6 Injection Site Reactions

Injection site reactions will be evaluated using a local injection-site symptom assessment (LISSA). Frequency and percentage distribution of the severity of each pre-specified symptom (pain, tenderness, erythema/redness and induration/swelling) will be presented by treatment group for each visit.

## **6.8** Pregnancy Test

Urine and serum pregnancy test for female subjects will be presented in data listings.

## 7. Pharmacokinetic, Biomarker, and Immunogenicity Data

# 8. Health Outcomes Data Analyses

[figure not shown]
Not applicable

# 9. Interim Analyses and Data Monitoring

No interim analyses are planned for this study.

# 13. Apendices

# 13.1 Appendix A: NASH Clinical Research Network NAFLD Activity Score and Fibrosis Score

[figure not shown]
		Lobular			
Steatosis	S Score	Inflammation	L Score	Hepatocyte Ballooning	B Score
< 5%	0	None	0	None	0
5%-33%	1	< 2	1	Few ballooned cells	1
34%-66%	2	2–4	2	Many ballooned cells	2
> 66%	3	> 4	3	_	

[figure not shown]
NAFLD = nonalcoholic fatty liver disease.

[figure not shown]
Note: NAFLD activity grade score = total score: S + L + B (range 0–8).

Fibrosis Stage	Score
0	No Fibrosis
1a	Zone 3, Mild
1b	Zone 3, Moderate
1c	Periportal Only
2	Zone 3 and Periportal
3	Bridging
4	Cirrhosis

[figure not shown]
# 13.2 Appendix B: SAS Programming Code for MCP-Mod Analysis

[figure not shown]

[figure not shown]
Page 30 of 36

[figure not shown]
Page 31 of 36

[figure not shown]
Page 32 of 36

Page 33 of 36

Page 34 of 36

Page 35 of 36

# 13.3 Appendix C: Simulation Parameters

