#### **Imputation**

Missing fibrosis responses are imputed 25 times to generate 25 complete data sets. The imputed values will be obtained using a logistic model with fixed effects for treatment group and baseline fibrosis stage. At the end of this step, all the 25 complete data sets contain the same non-missing values while the missing values are replaced by imputed values. The following is an example of SAS programming code to be implemented.

The random seeds to be used for this and all subsequent analyses are provided in Appendix C.

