## **Pooling**

The results from the 25 completed data sets obtained in the analysis step are combined for the inference. The pooled estimate of the multiplicity adjusted p-value for testing H0 vs H1 will be the median of the individual multiplicity adjusted p-values from the 25 completed data sets. The pooled estimate of the response rate along with its standard error and 95% CI for each dose level will be obtained using the method developed by Rubin (1987). The following is an example of SAS programming code to be implemented.

The null hypothesis H0 (Section 5.1.2) will be rejected and a statistically significant trend (i.e., an upward slope) of the fibrosis response across Aldafermin doses will be established if

- the pooled estimate of the multiplicity adjusted p-value obtained from the MI inference is ≤ 0.05 and;
- the pooled estimate of the response rate for Aldafermin 3 mg is higher than that for placebo.

The ITT analysis set will be used for these analyses.

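### The primary p-value is a median over only 25 imputed data sets, so for a borderline result its Monte Carlo error is large enough to set the verdict; at least 500 imputations would be better

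*SAP*

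**What the plan says.** SAP 5.1.5 (Imputation) states: "Missing fibrosis responses are imputed 25 times to generate 25 complete data sets". The imputation model is "a logistic model with fixed effects for treatment group and baseline fibrosis stage". On reproducibility it adds: "The random seeds to be used for this and all subsequent analyses are provided in Appendix C".

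Under Pooling the SAP sets the primary p-value: "The pooled estimate of the multiplicity adjusted p-value for testing H0 vs H1 will be the median of the individual multiplicity adjusted p-values". The null hypothesis is rejected if this pooled value is at or below 0.05 and "the pooled estimate of the response rate for Aldafermin 3 mg is higher than that for placebo".

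SAP 1.3 plans 38 subjects per arm with 15% drop-out at Week 24, so 32 per arm are observed and about 6 per arm are imputed.

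The visible text gives no reason for 25, no target for Monte Carlo error, and no rule for a pooled p-value close to 0.05. The contents of Appendix B (code) and of "Appendix C: Simulation Parameters" (seeds), and the details of the MCP-Mod test in 5.1.4, are not shown in the public copy.

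**The concern.** The trial's one primary efficacy test compares a single number with 0.05. That number is the median of 25 random draws, so it carries simulation error on top of sampling error. A fixed seed makes the result repeatable. It does not bring it closer to the value that a very large number of imputations would give on the same data (the converged p). If the error is not small beside the distance from 0.05, the same data with another equally acceptable seed could give the opposite conclusion. A reported p of 0.045 or 0.055 would then be hard to defend.

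**Working it through.** **Inputs.** From the SAP: 25 imputations, the median rule and the 0.05 threshold (5.1.5); 38 per arm, 15% missing, two-sided 5% and the response rates of Table 1 (1.3). Assumed: 25 F2 and 13 F3 subjects per arm, in line with the cap of about 65% F2 in Protocol 12.2. Also assumed, because the SAP's own test is not visible: a stand-in test, the maximum of six optimal contrasts on response proportions, one per Table 1 scenario, with a multivariate-normal critical value of 2.30.

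**Step 1: reproduce SAP Table 1** (32 per arm, 200,000 simulated trials per scenario).

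| Scenario (placebo / 0.3 / 1 / 3 mg) | SAP power | Stand-in |
|---|---|---|
| 15/16/19/50% | 92% | 93.4% |
| 15/18/30/50% | 90% | 91.4% |
| 15/20/42/50% | 93% | 93.3% |
| 15/32/39/50% | 85% | 85.7% |
| 15/36/45/50% | 87% | 88.4% |
| 15/43/48/50% | 90% | 90.1% |
| 15% in all arms | 5% | 4.9% |

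All are within 2 points, so the stand-in is a reasonable proxy for size and power.

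**Step 2: approximation by hand.** This treats the adjusted p as coming from a single two-sided z.

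- Ratio of between- to within-imputation variance: 0.15/0.85 = 0.176. SD of z between imputations: √0.176 ≈ 0.42.
- Standard error of a median of 25: 1.253 × 0.42/√25 ≈ 0.105 on the z scale.
- For a converged p of 0.05: z = 1.96 ± 1.96 × 0.105 = 1.96 ± 0.206, so p runs from about 0.030 to 0.079.
- With 500: 1.253 × 0.42/√500 ≈ 0.0235. Then z = 1.96 ± 0.046, so p runs from about 0.045 to 0.056.

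**Step 3: simulation.** 38 per arm with 6 missing; logistic imputation on treatment and fibrosis stage; 1,000 to 2,000 imputations per simulated trial; medians of m of these resampled. The first two result columns are for a converged p of 0.045–0.055. The third is the range of converged p for which either verdict has a 5–95% chance. The last is for the 15/32/39/50% scenario.

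| m | SE of median p | 95% of seeds | Seed-sensitive converged p | Two seeds disagree |
|---|---|---|---|---|
| 25 | 0.0125 | 0.031–0.079 | 0.032–0.073 | 2.0% |
| 100 | 0.0061 | 0.039–0.063 | 0.040–0.061 | 0.9% |
| 500 | 0.0028 | 0.045–0.055 | 0.045–0.056 | 0.4% |
| 1,000 | 0.0020 | 0.046–0.054 | 0.046–0.053 | 0.25% |

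Another variant of the stand-in gives an SE of about 0.011 at m = 25.

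Share of seeds giving p ≤ 0.05 with 25 imputations, by converged p:

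- 0.03–0.04: about 90–93%
- 0.045–0.050: about 58–61%
- 0.055–0.060: about 27–31%
- 0.07–0.08: about 4–7%

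Over a converged p of 0.04–0.06, about 30–36% of seeds fall on the wrong side of 0.05, against about 7–13% with 500, depending on the variant.

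**Step 4: how often it matters.** With 25 imputations, two seeds disagree in 0.9–2.0% of trials across the six Table 1 scenarios. Under weaker effects that are assumed and stand in neither document, the figure is 4.3% (15/20/25/35%) or 4.7% (15/22/27/35%).

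**Step 5: sensitivity to missingness.** The SE near 0.05 with 25 imputations is about 0.007–0.008 at 5% missing, 0.009–0.010 at 10%, 0.012–0.014 at 15% and 0.016–0.019 at 25%. If each adjusted p is itself obtained by resampling, that adds error of unknown size. For one p at 0.05 the standard error is √(0.05 × 0.95/B): 0.0069 for an assumed B = 1,000 and 0.0022 for B = 10,000.

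**The case against.** The strongest reply is that the plan already does what matters for integrity. The seeds are fixed in advance, so nobody can choose one after seeing the data. What is left is one arbitrary draw, and under the plan's own scenarios another draw would change the verdict in only 1–2% of trials. Protocol 12.5.1 also plans responder and non-responder imputation, missing-not-at-random analyses, and Full-Analysis and PP analyses, so a borderline result would not be read alone.

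Most of this stands. A reader might infer from the blank Appendix C that the seeds are unspecified or open to choice. The documents do not support that: 5.1.5 says that they are provided, and the missing page reflects the public copy. A reader might also infer that the seed decides the trial. It can do so only when the converged p lies at about 0.03–0.07. The supporting analyses give context for such a result but do not reduce the Monte Carlo error in the primary p-value.

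A second reply is that the converged median is not itself a sound benchmark, because the median ignores between-imputation variance. In the stand-in test with 15% missing, the median rule rejected a flat dose-response in 8.4–8.9% of trials, before the requirement that 3 mg exceed placebo. That is a separate question, to be checked with the SAP's own code. More imputations would not change it.

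**Conclusion.** The point holds as a minor, inexpensive improvement. Twenty-five imputations are few for a median p-value judged against a sharp threshold. With 15% missing, the standard error is about 0.011–0.0125 near 0.05, and for a converged p of about 0.03–0.07 the prespecified but arbitrary random stream can set the verdict. Overall this is uncommon: about 1–2% of trials under the Table 1 scenarios, and about 4–5% under a weaker effect that is assumed here.

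The sizes rest on a stand-in contrast test, since the SAP's MCP-Mod code, candidate models and any resampling counts are not visible. They also rest on missingness at the planned 15%. The documents do not support calling the fixed seeds a defect, or saying that the seed decides the trial in general.

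**What to change.** In SAP 5.1.5 (Imputation), replace 25 with at least 500 imputations for the primary MCP test, change the count under Analysis and Pooling to match, and keep the prespecified seeds. Under the plan's scenarios this cuts the standard error near 0.05 to about 0.003 and two-seed disagreement to about 0.2–0.5%. It reduces the Monte Carlo error but does not remove it.

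The cost is computing time: 500/25 = 20 times as many runs of a small four-arm binary test, with no effect on patients, data or design. The bootstrap standard errors of the Mod step need not be scaled up. Using the same number for the imputed secondary histology endpoints is optional. The change should be made before unblinding. The validity of the median as a pooling rule should be settled separately.
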